## 14.7. Study Records

The Investigator is responsible for preparing and maintaining adequate records to enable the conduct of the study to be documented. Study records include, but are not limited to, regulatory documentation (Section 14.7.1) and patient records (Sections 14.7.2 and 14.7.3).

#### 14.7.1. Regulatory Documentation

Prior to initiating the study, the Investigator will provide Leadiant Biosciences the following documents:

- A signed FDA Form 1572
- A current curriculum vitae for the Principal Investigator and each sub-investigator listed on the FDA Form 1572
- Copy of the current medical licenses for the Investigator and physician sub-investigators
- Written IRB approval of the protocol, informed consent form and any other material provided to potential study participants with information about the study (e.g., advertisements)
- A copy of the IRB-approved informed consent document and HIPAA authorization
- Current IRB membership list for the reviewing IRB and/or multiple project assurance number or an IRB organization number under the Federal Wide Assurance program ([www.ohrp.osophs.dhhs.gov](http://www.ohrp.osophs.dhhs.gov))
- A signed Investigator Protocol Agreement (Section 15 of study protocol)
- Completed financial disclosure form for the Investigator and all sub-investigators
- Local reference laboratory documentation, including current laboratory certification, current laboratory normal values, and directors CV

During the course of the study, the Investigator will maintain current records to document regulatory compliance with the study including: the study protocol and amendments, all versions of the Investigators Brochure in effect during study conduct, signed Investigator Agreement protocol page(s), FDA 1572 forms, curricula vitae of the Investigator and sub-investigators, medical licenses of the Investigator and physician sub-investigators, financial disclosure of the Investigator and sub-investigators, IRB approvals of the protocol, protocol amendment(s), informed consent form(s), IRB membership list, IRB-approved informed consent form(s), IRB correspondence, protocol deviations, study logs (as provided by Leadiant Biosciences), drug dispensing and accountability records, safety reports, and all correspondence pertaining to the conduct of the study. Regulatory documentation will be reviewed by Leadiant Biosciences or its representatives during monitoring visits to assure regulatory compliance.

#### 14.7.2. Source Documents

The Investigator will maintain records separate from the case report forms in the form of clinical charts, medical records, original laboratory, radiology and pathology reports, pharmacy records, patient diary cards, etc. The Investigator will document in the clinic chart or medical record the name and number of the study and the date on which the patient signed informed consent prior to the patient's participation in the study. Source documents must completely reflect the nature and extent of the patient's medical care, and must be available for verification against case report form entries when the Leadiant Biosciences or its representatives visit the investigational site. All information obtained from source documents will be kept in strict confidentiality.

#### 14.7.3. Case Report Forms

All site-generated study data will be entered either onto case report forms (CRFs) supplied by Leadiant Biosciences or into an electronic Case Report Form (eCRF) via an electronic data capture (EDC) system. The CRFs/eCRFs are not to be used as the primary method for collection of study data (unless otherwise described in this section of the study protocol) and CRF/eCRF entries must be supported by source documents maintained by the Investigator. Only those site staff so authorized at the initiation of the study may enter data onto the case report forms or into an EDC system.

For those studies using paper CRFs, all entries must be legible and made in black pen. If an entry error is made, a single line will be placed through the incorrect entry. The correct entry will then

be made, with the correction dated and initialed by the person making the entry. Any corrections to data entered into the CRF must be made in such a way that the original entry is not obscured. Resolutions to data clarification forms (DCFs) issued by Leadiant Biosciences or its designated data management contractor will be maintained with the CRFs for each patient.

The Investigator is responsible for the completeness and accuracy of all CRF/eCRF data as certified by the Investigator's dated signature on designated CRF/eCRF pages.

#### **14.7.4. Access to Study Records**

The Investigator will make available all records pertaining to the conduct of this study to Leadiant Biosciences and its representatives, and auditors from domestic and foreign regulatory authorities to facilitate monitoring visits and study audits.

#### **14.7.5. Records Retention**

The Investigator will retain the records of the study for 15 years, or for 2 years following the date that a marketing application for the study drug is approved, or if no marketing application is filed, or if such an application is not approved, for 2 years after the IND has been closed. Leadiant Biosciences will notify Investigators when retention of study records is no longer required. All study records must be maintained in a safe and secure location that allows for timely retrieval, if needed.

Study records that must be retained include copies of case report forms, signed informed consents, regulatory documentation, source documents, clinic charts, medical records, laboratory results, radiographic reports, and other study-specific documentation.

Should the Investigator relocate or retire, or should there be any changes in the archival arrangements for the study records, Leadiant Biosciences must be notified. The responsibility for maintaining the study records may be transferred to another suitable individual, but Leadiant Biosciences must be notified of the identity of the individual assuming responsibility for maintaining the study records and the location of their storage. If no other individual at the investigational site is willing to assume this responsibility, Leadiant Biosciences will assume responsibility for maintaining the study records.

### **14.8. Publication Policy**

Publication of study data is addressed in the Clinical Study Agreement between Leadiant Biosciences and the Investigator and/or Institution.

### **14.9. Financing and Insurance**

Financing and Insurance are addressed in the Clinical Study Agreement between Leadiant Biosciences and the Investigator and/or Institution.

| Procedure   | EZN-2279 Treatment Period (Weeks 14 through 21) |           |           |           |           |           |           |           | EZN-2279 Maintenance g | End of Study/Early Discontinuation | 30-Day Early Discontinuation Follow-up i |
|---|---|-----------|-----------|-----------|-----------|-----------|-----------|-----------|-----------------------------------|------------------------------------|---|
|   | Week T-14                                       | Week T-15 | Week T-16 | Week T-17 | Week T-18 | Week T-19 | Week T-20 | Week T-21 |                                   |                                    |   |
|   | Day 92  | Day 99    | Day 106   | Day 113   | Day 120   | Day 127   | Day 134   | Day 141   |                                   |                                    |   |
| Informed assent/consent   |   |           |           |           |           |           |           |           |                                   |                                    |   |
| Demographics  |   |           |           |           |           |           |           |           |                                   |                                    |   |
| Disease background/history
Prior Treatments
Adagen ® Dose
Adagen ® AEs
Infectious complications
Hospitalizations |   |           |           |           |           |           |           |           |                                   |                                    |   |
| Medical history   |   |           |           |           |           |           |           |           |                                   |                                    |   |
| Medication history  |   |           |           |           |           |           |           |           |                                   |                                    |   |
| Physical examination  |   |           |           | X         |           |           |           | X         | X                                 | X                                  | X   |
| Vital signs   |   |           |           | X         |           |           |           | X         | X                                 | X                                  | X   |
| Performance status  |   |           |           | X         |           |           |           | X         | X                                 | X                                  | X   |
| Height, weight, growth curve  |   |           |           | X         |           |           |           | X         | X                                 | X                                  | X   |
| Pregnancy test  |   |           |           |           |           |           |           |           |                                   |                                    |   |
| Serum chemistry   |   |           |           | X         |           |           |           | X         | X                                 | X                                  | X   |
| Hematology  |   |           |           | X         |           |           |           | X         | X                                 | X                                  | X   |
| Urinalysis  |   |           |           |           |           |           |           | X         | X                                 | X                                  | X   |
| Total trough erythrocyte dAXP   |   | X         |           | X         |           | X         |           | X         | X                                 | X                                  |   |
| Trough ADA activity   |   | X         |           | X         |           | X         |           | X         | X                                 | X                                  |   |
| Full PK profile j  |   |           |           |           |           |           |           |           |                                   |                                    |   |
| B-/T-/NK-lymphocyte subset  |   |           |           |           |           |           |           | X         | X                                 | X                                  |   |
| Quantitative immunoglobulins  |   |           |           |           |           |           |           | X         | X                                 | X                                  |   |
| Antibody titers (binding, neutralizing), anti-PEG antibodies  |   |           |           |           |           |           |           | X         | X                                 | X                                  |   |
| Clinical status
Infectious complications
Hospitalizations   |   | X         |           | X         |           | X         |           | X         | X                                 | X                                  |   |
| Overall Survival  |   |           |           |           |           |           |           | X         | X                                 | X                                  |   |
| Adverse Events  | ←----->   |           |           |           |           |           |           |           |                                   |                                    |   |
| Concomitant medications/procedures  |   | X         |           | X         |           | X         |           | X         | X                                 | X                                  | X   |
| Adagen ® administration (± 1 day)  |   |           |           |           |           |           |           |           |                                   |                                    |   |
| EZN-2279 administration (± 1 day)   | X   | X         | X         | X         | X         | X         | X         | X         | X h                    |                                    |   |

g - assessments every 13 weeks ± 3 weeks; h – dosing of EZN -2279 continues once a week ± 1 day; i – only for patients who discontinue the study early

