### 7.1.1. Study Periods

Patient participation in the study will be defined by the four distinct study periods defined below:

- Screening (up to 28-days prior to start of Adagen® Lead in dosing) – This period starts at the time of the initial screening procedure through administration of the first dose of Adagen® in the lead in period. Note: patients will continue to receive his/her prescribed dose of Adagen® during this period.
- Adagen® Lead-in – This period starts with the initial dose of study-required Adagen® dosing through the start of EZN-2279 study treatment. This period will be a minimum of 3 weeks.
- EZN-2279 Study Treatment – This period starts with the initial dose of EZN-2279 through completion of at least 21 weeks of EZN-2279 dosing.
- EZN-2279 Maintenance – This period begins after completion of the EZN-2279 study period and continues until the end of the study (full regulatory approval of EZN-2279 or early study termination).

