### **9.3. Exclusion Criteria**

Patients meeting any of the following exclusion criteria will not be eligible for enrollment.

1. Autoimmunity requiring immunosuppressive treatment.
2. Patients with detectable neutralizing anti-Adagen® antibodies at screening evaluation.
3. Severe thrombocytopenia (platelet count  $< 50 \times 10^9/\text{L}$ ).
4. Current participation in other therapeutic protocols for ADA-deficient combined immunodeficiency.

5. Current or prior participation in another clinical study with an investigational agent and/or use of an investigational drug in the 30 days before study entry.
6. Known planned participation in a gene-therapy study for the planned duration of this study.
7. Any condition that, in the opinion of the PI, makes the patient unsuitable for the study.
8. Inability or unwillingness to administer Adagen® or EZN-2279 on a one time per week regimen.
9. Inability to comply with the study protocol.
10. Female patients who are pregnant or lactating.
11. Female patients who are breast-feeding.
12. Female patients of childbearing potential who are not using an FDA approved birth control method.

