### 10.4.3. Laboratory Assessments

The following laboratory evaluations will be performed by the site's local laboratory as indicated in Sections 11.1 through 11.5 and Appendix 1.

- Hematology: Hemoglobin, hematocrit, WBC count, differential (includes at least: neutrophils [include bands], lymphocytes, monocytes, eosinophils, and basophils), and platelet count.
- Serum chemistry: Bicarbonate, blood urea nitrogen (BUN), calcium, chloride, creatinine, glucose, magnesium, phosphate, potassium, sodium, and total protein, albumin, alkaline phosphatase, ALT, AST, and total bilirubin.
- Urinalysis: Macroscopic (bilirubin, blood, glucose, ketones, leukocyte esterase, nitrite, pH, protein, specific gravity, and urobilinogen). Microscopic examination will include red blood cells (RBCs), WBCs, bacteria, and casts.
- Serum or urine pregnancy test: Only for female patients of child-bearing potential.

If a laboratory assessment has been performed within the specified protocol window as part of standard of care by a laboratory listed on the FDA 1572 form, it does not need to be repeated for the purpose of the protocol. The laboratory assessment result will be included on the CRF for the study.

Following the start of study treatment clinically meaningful laboratory abnormalities will be reported as an adverse event.

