### 11.1. Screening

Patients who fulfill all of the inclusion criteria and none of the exclusion criteria may be entered into the study.

The following evaluations are to be performed within 28 days before start of the Adagen® Lead-in period unless otherwise indicated.

- Informed assent/consent
- Obtain patient history and baseline characteristics
  - Demographics
  - Disease background and history
  - Assessment of AEs/toxicities the patient has experienced while on Adagen® treatment
  - Assessment of infectious complications and hospitalizations within the past 12 months
  - Medical history
  - Medication history
- Physical examination
- Vital signs
- Height and weight for growth assessment
- Performance status score
- Urine or serum pregnancy test for females of childbearing potential must be performed within 7-days before starting Adagen® Lead-in.
- Safety Lab
  - Hematology
  - Serum chemistry
  - Urinalysis
- Immunogenicity - Adagen® antibody titers (i.e., neutralizing and binding antibodies) and anti-PEG antibodies

Patients passing screening assessment will enter the Adagen Lead-in phase of the study.

For patients currently maintained with Adagen® on a 1 time per week dosage regimen, the following additional laboratory assessments will be performed to determine whether an Adagen® dosage adjustment when entering the Adagen® Lead-in phase is required:

- Total erythrocyte dAXP from a trough blood sample
- Trough plasma ADA activity

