#### 12.5. Reporting of Pregnancy

If a patient becomes pregnant or is found to be pregnant while on the study, the Leadiant Biosciences medical monitor or designee will be contacted to discuss the management of the patient, which may include discontinuation of study drug.

Although pregnancy is not a serious adverse event all pregnancies occurring during this study will be reported to the Leadiant Biosciences Drug Safety within 48 hours of becoming aware of the pregnancy and complete and submit a pregnancy report form.

All pregnancies will be followed until delivery or pregnancy termination for maternal and fetal outcomes.

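### The only scheduled pregnancy test precedes the Adagen lead-in; none is scheduled at the switch to EZN-2279, during about 2 to 3 years of dosing, or at study end

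*Protocol*

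**What the plan says.** Protocol Section 11.1 gives the only dated requirement: "Urine or serum pregnancy test for females of childbearing potential must be performed within 7-days before starting Adagen" lead-in. Section 10.4.3 names the test ("Serum or urine pregnancy test: Only for female patients of child-bearing potential") but leaves its timing to Sections 11.1 to 11.5 and Appendix 1.

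The later procedure lists do not include it: weekly lead-in visits (11.2.2), Adagen pharmacokinetic Day 1 (11.2.3.1), Week T-1 before the first EZN-2279 dose (11.3.1), the remaining treatment weeks to T-21 (11.3.22), maintenance (11.4), study completion (11.5) and the 30-day follow-up (11.5.1). SAP Table 1 marks the test in the Screening column only. In Appendix 1, the page from Week T-14 onward carries the row "Pregnancy test" with every cell empty.

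Four other provisions bear on this:
- Exclusion 10 in Section 9.3: "Female patients who are pregnant or lactating".
- Exclusion 12 in the same section: "Female patients of childbearing potential who are not using an FDA approved birth control method". The synopsis list stops at number 11 and lacks it.
- Section 11.2.2: a patient may go on to the Adagen pharmacokinetic assessment only if the other selection criteria are still satisfied.
- Section 12.5: a management and reporting rule that applies "If a patient becomes pregnant or is found to be pregnant while on the study", with a report due within 48 hours of awareness and follow-up to outcome.

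**The concern.** The test is tied to the start of the marketed product, not to the start of the investigational one. Section 5.3.2 states that EZN-2279 has not been studied clinically. Section 11.2.2 expects the selection criteria still to hold when the patient leaves the lead-in, but no scheduled procedure can confirm this for pregnancy. A conception shortly before or during the lead-in could go unnoticed at the switch, and one during maintenance could go unnoticed for some time.

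Patient safety is at stake first, and then the completeness of the pregnancy information that Section 12.5 asks for. Childbearing status can also change. Sections 9.2 and 9.3 set no age limits, and Section 10.6.1 provides for patients under 10. A girl who is outside the test's scope at screening could enter it during years of dosing and never be tested.

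**Working it through.** **Plan's own duration figure.** Section 7.4.1 gives about 3 years of study treatment for the first patient and about 2 years for the last. It assumes 12 months of enrollment and 18 months for submission and approval. The 3-week lead-in plus 21 treatment weeks is 24 weeks, or about 5.5 months.
- Last patient: 5.5 + 18 = 23.5 months, about 1.96 years.
- First patient: 5.5 + 18 + 12 = 35.5 months, about 2.96 years.

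The stated figures are reproduced, and they include the lead-in.

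**Gap from the test to the first EZN-2279 dose.** Section 7.1.1 says of the lead-in: "This period will be a minimum of 3 weeks". Gap = lead-in length + 0 to 7 days.
- Minimum lead-in: 21 + 0 = 21 days to 21 + 7 = 28 days.
- With the optional lead-in Weeks 3 and 4 and the pharmacokinetic week (assumed 5 weeks in all): 35 to 42 days.
- Maximum: none stated. Section 11.2.2 lets re-adjustment repeat, and Section 10.7.2 spaces Adagen adjustments at least 2 weeks apart.

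**Gap from the test to Week T-21.** Day 141 is 140 days after the first EZN-2279 dose. With the minimum lead-in the gap is 21 + 140 = 161 days to 28 + 140 = 168 days.

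**EZN-2279 dosing without a scheduled test.** Leave out the lead-in, and take 18 months as about 78 weeks and 30 months as about 130 weeks.
- Last patient: 21 + 78 = 99 weeks.
- First patient: 21 + 130 = 151 weeks.

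**Maintenance visits in that time.** Section 11.4 places visits at Week 21 + 13k, which gives Weeks 34, 47, and so on to 190 for k = 1 to 13, as listed. By Week 99 there are 6 visits, and by Week 151 there are 10. Scheduled pregnancy tests after the first EZN-2279 dose: 0.

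**Where urine is already taken.** Urinalysis is listed at T-1 (11.3.1), T-21 (11.3.22), every maintenance visit (11.4) and study completion (11.5).

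**Limit of the evidence.** The Appendix 1 page available for this review starts at Week T-14. For earlier visits the finding rests on Section 11 and SAP Table 1, which agree.

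**The case against.** The strongest reply is that the rules are compatible as written. Exclusion 10 governs enrollment, and the screening test verifies it there. Exclusion 12 requires contraception at entry. Section 12.5 starts its clock when someone becomes aware of a pregnancy. A reader might infer that Section 12.5 promises surveillance and that the schedule breaks that promise. The text does not support this, because the section covers reporting and follow-up of known pregnancies.

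Detection is also not left to self-report alone. History is updated and an examination done at Adagen pharmacokinetic Day 1. Examination and weight recur at T-1, every 4 weeks in the treatment period and at each maintenance visit, and Section 10.4.4 provides for open questioning. None of these is a pregnancy test, however, and early pregnancy can escape all of them.

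A reader might also infer from Section 5.3.1.3 that no reproductive toxicology exists. That does not follow, because Section 5.2 calls these brief summaries and refers to the Investigator's Brochure for detail.

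What the reply does not answer is Section 11.2.2, which expects the criteria still to hold after the lead-in. Nor does it answer the lack of any later check on contraception.

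**Conclusion.** The point stands as a gap in scheduled safety assessment. Pregnancy is tested once, 21 to 28 days or more before the first EZN-2279 dose, and not again over roughly 99 to 151 weeks of dosing. Those weeks rest on the protocol's own timeline and a 3-week lead-in.

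A reader might take the stated 2 to 3 years as 104 to 156 weeks of EZN-2279. Because the stated period includes the Adagen lead-in, that count is slightly too high. A reader might also describe every switch as a first human dose; on the documents this is literal only for the first patient treated.

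The size is bounded. Only females of childbearing potential are affected, their number among about six patients is not given, and contraception at entry lowers the risk. The primary endpoint and its analysis do not change. The point merits correction because the omission concerns safety and the remedy is small.

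**What to change.** Reconcile Protocol Sections 9.3, 10.4.3, 11.1, 11.2.2 and 12.5 with the schedule. For females of childbearing potential, mark the existing pregnancy-test row in Appendix 1 and SAP Table 1, and add the test to the lists in Sections 11.3.1, 11.3.22, 11.4 and 11.5, where urine is already collected for urinalysis. State that childbearing status is updated as patients age. Align the synopsis exclusions with Section 9.3, so that the contraception criterion appears in both.

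Any consequence of a result for dosing is for the sponsor to settle with Section 12.5; no dosing rule is proposed here. The analysis needs nothing new, since SAP Section 7.4 already lists pregnancy test results.

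The cost is the test kits, with no added visit or blood draw, plus a written amendment with IRB approval under Section 14.1.1 and re-consent if the consent form changes.
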